#### **Medtronic Controlled Information**

[figure not shown]
# Prestige LP™2 Metal Concentration Clinical Investigation Plan

MDT16060SD1701

Version 6.0, 08-JUL-2019

Page 20 of 46

Medtronic

**Table 1:** Prestige LP™ Cervical Disc Device Sizes

Catalog Number	Size
6972250	5mm x 12mm
6972450	5mm x 14mm
6972650	5mm x 16mm
6972260	6mm x 12mm
6972460	6mm x 14mm
6972660	6mm x 16mm
6972860	6mm x 18mm
6972470	7mm x 14mm
6972670	7mm x 16mm
6972870	7mm x 18mm
6972480	8mm x 14mm
6972680	8mm x 16mm
6972880	8mm x 18mm

## 7.3 Study Product Packaging and Labeling

The Prestige LP™ Cervical Disc is provided in a sterile package ready for use. The Prestige LP™ Cervical Disc device is placed in a Polyethylene-terephthalate-glycol (PETG) retainer and lid to hold the inferior and superior components in place. The retainer assembly and device are placed packaged in a dual PETG tray with Tyvek configuration. The assembly and subject labels are placed inside a carton and sealed. The product label is applied to the outside of the carton.

## 8 Selection of Subjects

### 8.1 Study Population

A total number of 30 subjects will be enrolled in this study.

#### Medtronic Controlled Information

This document is electronically controlled

056-F275, vA Clinical Investigation Plan Template

## **8.2 Subject Enrollment**

A subject is considered enrolled in this clinical study at the time at which he/she signs the subject Informed Consent. All subjects must sign the Informed Consent prior to undergoing any evaluations or procedures that are purely research-related (defined as those that would not be done if the subject was not participating in this study) or collection of study data.

## **8.3 Inclusion Criteria**

A subject must meet all the following inclusion criteria to participate in this study:

- I.1 Has cervical degenerative disc disease at two (2) contiguous cervical levels (from C3 to C7) requiring surgical treatment and involving intractable radiculopathy, myelopathy or both;
- I.2 Has a herniated disc and/or osteophyte formation at each level to be treated that is producing symptomatic nerve root and/or spinal cord compression. The condition is documented by patient history (e.g., neck and/or arm pain, functional deficit and/or neurological deficit), and the requirement for surgical treatment is evidenced by radiographic studies (e.g., CT, MRI, x-rays, etc.);
- I.3 Has been unresponsive to non-operative treatment for at least six weeks or has the presence of progressive symptoms or signs of nerve root/spinal cord compression in the face of continued non-operative therapy;
- I.4 Has no previous surgical intervention at the involved levels or any other planned/staged surgical procedure at the involved levels
- I.5 Has preoperative neck pain score  $\geq 8$  based on the preoperative Neck and Arm Pain Questionnaire;
- I.6 Must be at least 18 years of age and be skeletally mature at the time of surgery;
- I.7 If a female of childbearing potential, subject is non-pregnant, non-nursing, and agrees not to become pregnant during the study period;
- I.8 Is willing to comply with the study plan and sign the Subject Informed Consent Form.

## **8.4 Exclusion Criteria**

A subject will be excluded from participating in this study for any of the following reasons:

- E.1 Has a cervical spine condition other than symptomatic cervical degenerative disease requiring surgical treatment at the involved levels;
- E.2 Has documented or diagnosed cervical instability relative to contiguous segments at either level, defined by dynamic (flexion/extension) radiographs showing:
  - a. Sagittal plane translation  $> 3.5$  mm, or
  - b. Sagittal plane angulation  $> 20^\circ$
- E.3 Has more than two cervical levels requiring surgical treatment;

---

### **Medtronic Controlled Information**

# Prestige LP™2 Metal Concentration Clinical Investigation Plan

MDT16060SD1701

Version 6.0, 08-JUL-2019

Page 22 of 46

Medtronic

- E.4 Has severe pathology of the facet joints of the involved vertebral bodies;
- E.5 Has had previous surgical intervention at either one or both of the involved levels;
- E.6 Has been previously diagnosed with osteopenia or osteomalacia;
- E.7 Has any of the following that may be associated with a diagnosis of osteoporosis (If "Yes" to any of the below risk factors, a DEXA Scan will be required to determine eligibility.):
  - a. Postmenopausal non-Black female over 60 years of age who weighs less than 140 pounds.
  - b. Postmenopausal female who has sustained a non-traumatic hip, spine or wrist fracture.
  - c. Male over the age of 70.
  - d. Male over the age of 60 who has sustained a non-traumatic hip or spine fracture. If the level of BMD is a T score of -3.5 or lower (i.e., -3.6, -3.7, etc.) or a T score of -2.5 or lower (i.e., -2.6, -2.7, etc.) with vertebral crush fracture, then the subject is excluded from the study.
- E.8 Has the presence of spinal metastases;
- E.9 Has overt or active bacterial infection, either local or systemic;
- E.10 Has chronic or acute renal failure or prior history of renal disease;
- E.11 Has a documented allergy or intolerance to titanium, or a titanium alloy;
- E.12 Is mentally incompetent (if questionable, obtain psychiatric consult);
- E.13 Is a prisoner;
- E.14 Is pregnant;
- E.15 Has received drugs that may interfere with bone metabolism within two weeks prior to the planned date of spinal surgery (e.g., steroids or methotrexate), excluding routine perioperative anti-inflammatory drugs;
- E.16 Has history of an endocrine or metabolic disorder known to affect osteogenesis (e.g., Paget's Disease, renal osteodystrophy, Ehlers-Danlos Syndrome, or osteogenesis imperfecta);
- E.17 Has a condition that requires postoperative medications that interfere with the stability of the Implant, such as steroids. (This does not include low-dose aspirin for prophylactic anticoagulation and routine perioperative anti-inflammatory drugs.);
- E.18 Has received treatment with an investigational therapy within 28 days prior to implantation surgery or such treatment is planned during the 16 weeks following implantation.
- E.19 Is currently taking or has had chronic usage of certain prescription medications (e.g., Cloxacillin, and antibiotic used for prophylaxis against surgical infections, and/or Clotrimazole).

---

## Medtronic Controlled Information

## 8.5 Withdrawal Criteria

A subject may be withdrawn, if any of the following occur during the study:

- Subject refuses treatment
- Subject requests withdrawal from the study
- Subject withdraws consent
- AE makes the continuation of the subject impossible or inadvisable.
- Subject lost to follow-up.
- Subject discovered after enrollment not to have met the protocol entrance criteria.
- Subject refuses to comply with required study procedures.
- Use of any additional experimental drug or device or participation in another clinical study.
- The study Sponsor terminates the Investigator site or the study.

A subject may end his/her participation in a study at any time. If a subject withdraws, the Investigator is to make a reasonable effort to determine the reason for the subject's withdrawal from the study and to complete termination procedures. The clinical site will make a minimum of three (3) attempts to contact subjects who miss a scheduled study visit. Telephone calls, registered letters, and offers of transportation to the study site are considered reasonable effort. Documentation of attempts to reach the subject is to be document in the subject's medical and study record.

Subjects who withdraw from the study will not be replaced. Subjects who request withdrawal from the study will be asked their reason(s). Reason(s) for subject withdrawal will be recorded on the electronic case report form (eCRF) for all subjects that sign the informed consent.

If voluntary withdrawal occurs, the follow-up of these subjects will be according to the standard of care at the site. Data collection according to the study protocol will discontinue for subjects who withdraw and/or are withdrawn.

## 8.6 Strategies for Recruitment and Retention

Original Investigational Sites from the Prestige LP™ Two-Level IDE Study (P04-12) will be contacted to inform the Investigators and Sub-Investigators of this study and assess his/her willingness to participate. If up to five qualified sites cannot be selected from the original sites in the previous two-level study, other potential sites will be contacted and evaluated for participation.

## 9 Study Procedures and Visits

A narrative description of the various evaluations performed at each visit follows, organized by study phase. Study visits have been designed to occur on a schedule consistent with the standard of care for this type of treatment.

### Medtronic Controlled Information

# Prestige LP™2 Metal Concentration Clinical Investigation Plan

MDT16060SD1701

Version 6.0, 08-JUL-2019

Page 24 of 46

Medtronic

All subjects must give their informed consent in accordance with the informed consent regulations in Title 21 of the Code of Federal Regulations (CFR) 50.

## 9.1 Schedule of Events

**Table 2: Schedule of Study Assessments**

Procedure	Pre-/Peri-operative		6 wks. ±2 wks.	3mos. ± 2 wks.	6 mos. ± 1 mo.	12 mos. ± 2mo.	Study Exit
	Pre-operative	Surgery/ Hospital Discharge					
Preoperative Information							
Confirm patient eligibility	X						
Obtain informed consent	X						
Obtain HIPAA Authorization	X						
Case Report Forms							
Informed Consent	X						
Inclusion/Exclusion Criteria	X						
Demographics	X						
Medical and Surgical History	X						
Neurological Status	X		X	X	X	X	
Blood Collection for Metal Concentration Testing	X		X			X	
Neck and Arm Pain Questionnaire	X		X	X	X	X	
Surgery Data		X					
Device Identification		X					
Hospital Discharge		X					
Subject Visits			X	X	X	X	
Medications	X						
SF-36 PCS Health Survey	X		X	X	X	X	
Neck Disability Index	X		X	X	X	X	
Study Exit							X
Secondary Surgery Intervention (if applicable)			X	X	X	X	

### Medtronic Controlled Information

This document is electronically controlled

056-F275, vA Clinical Investigation Plan Template

# Prestige LP™2 Metal Concentration Clinical Investigation Plan

MDT16060SD1701

Version 6.0, 08-JUL-2019

Page 25 of 46

Medtronic

Adverse Event (if applicable)		X	X	X	X	X	
Protocol Deviation (if applicable)	X	X	X	X	X	X	
Device Deficiency (if applicable)		X	X	X	X	X	
DEXA Scan*	X						

\*A DEXA Scan was only required if the patient had a risk factor that may be associated with a diagnosis of osteoporosis.

## 9.2 Screening Procedures

After preliminary screening, if the subject is deemed eligible for further consideration in this study, the following procedures will be performed:

- The subject will be presented full information about the clinical study and asked if he/she would like to participate.
- If the subject agrees, he/she will be asked to sign the Informed Consent Form (ICF) and Health Insurance Portability Accountability Act (HIPAA) authorization form. No study procedures will be carried out until the subject has signed the ICF/HIPAA form(s).

Once the ICF/HIPAA form(s) are signed, the following procedures will be carried out:

- A copy of the signed ICF/HIPAA form(s) will be provided to the subject and/or to his/her legal representative.
- The subject will be evaluated for any remaining eligibility questions per the inclusion/exclusion criteria.
- The subject will be assigned a unique, sequential clinical study number.

NOTE: Screening and enrollment can both occur at one visit, or they can be split into multiple visits.

If after enrollment, the subject is discovered not to have met the study entrance criteria, as defined in the protocol, the subject will be exited from the study.

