### **Medtronic Controlled Information**

the subject will not be followed for efficacy and will not be counted in the total number of study subjects.

Follow up visits for the duration of the study period are required. If a subject is discontinued from the surgery after surgery, follow up visits will not be continued.

For a subject to be identified as discontinued, the following two conditions must be met: 1) the subject or his/her representative must notify the investigational site in writing, by telephone, or in person, and 2) no data is obtained on the subject after notification of discontinuation. The reason for the discontinuation will then be recorded on the Subject Disposition Electronic Case Report Form. Missed visits after discontinuation in the study will not constitute a protocol deviation.

Subjects who fail to return for follow up visits or who do not respond to efforts in scheduling evaluations will not be considered discontinued unless the study site has been officially notified of discontinuation.

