7.1.3.2 Per-Protocol Analysis Dataset

Per-protocol analysis dataset is the subset of the primary analysis dataset. Per-protocol analysis will be performed for the subjects who received the treatment of the PRESTIGE LP™ investigational devices at two contiguous levels but had no major protocol deviations, such as violation of inclusion and exclusion criteria or receiving different treatments other than intended treatment. Per-protocol analysis will only be carried out for overall success status.

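### Protocol 9.2 and 8.5 let implanted, still-consenting subjects leave data collection, mandatorily under 9.2 for late-found ineligibility, so the 12-month serum and later safety data can be lost

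*Protocol*

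**What the plan says.** **Point of enrollment.** Protocol 8.2: "A subject is considered enrolled in this clinical study at the time at which he/she signs the subject Informed Consent". Protocol 8.1: "A total number of 30 subjects will be enrolled in this study".

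**Late-found ineligibility.** Protocol 9.2 has a rule for the time following enrollment: when "the subject is discovered not to have met the study entrance criteria, as defined in the protocol, the subject will be exited from the study". Section 8.5 lists the same event among the things that may lead to withdrawal during the study. The verb is mandatory in 9.2 and permissive in 8.5.

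**Other triggers in 8.5.** The list includes "AE makes the continuation of the subject impossible or inadvisable" and participation in another clinical study or use of another experimental product. Both are permissive.

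**Consequence.** Protocol 8.5: "Data collection according to the study protocol will discontinue for subjects who withdraw and/or are withdrawn". Withdrawn subjects are not replaced. Section 9.6 adds that visits stop for a subject discontinued after surgery. Section 11.2 ends adverse event follow-up at discontinuation if that comes first.

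**Text pointing the other way.** Section 6.2 runs the study until every enrolled subject reaches 12 months. Section 11.1.2 follows subjects with a malignancy to study completion, and 11.1.3 follows all subjects with a secondary surgery at an index level.

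**Analysis.** SAP 7.1.3.1 keeps implanted subjects in the primary set unless they exit with no post-operative follow-up. SAP 7.1.3.2 defines the per-protocol set as those in the primary set who were treated "but had no major protocol deviations, such as violation of inclusion and exclusion criteria". SAP 7.4 analyses observed data only.

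**The concern.** The primary objective is serum titanium, vanadium and aluminum in implanted patients. After surgery there is no study treatment left to stop, only observation of a device that stays in place. A rule that ends observation because an entry criterion was found to be unmet does not change the subject's exposure; it only removes the data.

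Serum is drawn after surgery at 6 weeks and 12 months only (Table 2). An exit between those visits costs half of that subject's post-operative serum and the later part of the safety record. If the exit is triggered by an adverse event, the missing values may belong to the subjects whose course matters most in a post-approval safety study. With no replacement and no imputation, nothing later in the plan makes up for this.

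**Working it through.** There is no plan figure to reproduce: the 30 subjects have no alpha, power, effect size, SD or dropout rate behind them. The check is mainly textual, with an illustration of size.

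**1. Does the exit reach past surgery?** Enrollment is consent (8.2), so the period after enrollment covers the time before and after implantation. The 9.2 sentence closes the screening section, which suggests screen failures. But 8.5 lists the same trigger among events during the study, and no passage exempts implanted subjects.

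**2. What is lost, by time of exit?**

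| Exit for late-found ineligibility | Serum kept | Primary set under SAP 7.1.3.1 |
|---|---|---|
| Before implantation | Any pre-operative draw | Not included; nothing relevant lost |
| After implantation, before any follow-up | Pre-operative only | Not included |
| After the 6-week draw, before the 12-month draw | Pre-operative and 6-week | Included, no 12-month value |
| After the 12-month draw | All | Included |

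The two middle rows are the problem.

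**3. Precision.** Let n be the subjects with a 12-month value. Thirty is an upper limit, because it counts consents, not implants. The 95% half-width for a mean paired change, in SD units, is t(0.975, n−1)/√n. The one-sided 95% upper bound for an outcome with zero events is 1 − 0.05^(1/n). The numbers lost are assumed.

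| Lost | n | Half-width (SD) | Zero-event upper bound |
|---|---|---|---|
| 0 | 30 | 0.373 | 9.5% |
| 1 | 29 | 0.380 | 9.8% |
| 3 | 27 | 0.396 | 10.5% |
| 6 | 24 | 0.422 | 11.7% |

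**4. Selective loss, primary measurement.** Suppose k of 30 subjects are lost and their mean 12-month change is D SD above that of the rest. The full mean exceeds the observed mean by kD/30, so the bias is −kD/30.

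- D = 1: −0.03, −0.10 and −0.20 SD for k = 1, 3 and 6.
- D = 2: −0.07, −0.20 and −0.40 SD for the same k.

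Both k and D are assumed.

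**5. Selective loss, overall success (secondary).** Assume 24/30 = 80.0% true successes and that those lost would have failed and leave the denominator. One lost gives 24/29 = 82.8%, two give 24/28 = 85.7%, three give 24/27 = 88.9%. SAP 7.1.3.1 carries data forward for secondary surgery failures only. The SAP has no rule for a subject whose serious implant-related event has already made them a failure and who is then withdrawn. Whether that subject stays in the 12-month denominator is not stated.

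**The case against.** The best reply is that the rules are narrower than they look, and much of it stands. Only the 9.2 exit is mandatory. The adverse event item in 8.5 is permissive and has a high threshold. Data collected before exit are kept, and the life-table analyses use follow-up up to exit. Malignancy and index-level secondary surgery subjects are to be followed. The natural use of the 9.2 sentence is a screen failure after consent. None of this supplies the missing limit to the time before implantation, and 8.5 makes no exception for the subjects whom 11.1.2 and 11.1.3 say are followed.

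Some stronger readings are tempting but not supported:

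- **SAP 7.1.3.2 contradicts 9.2.** A reader might infer that violators kept in the primary set cannot exist if 9.2 has removed them. But leaving the study is not leaving the dataset: a violator exited after a post-operative visit stays in the primary set with observed data. Nor does the comparison of the two sets become meaningless; the per-protocol analysis covers overall success only.
- **E.18 contradicts 8.5.** E.18 excludes a subject if "such treatment is planned during the 16 weeks following implantation", while 8.5 permits withdrawal for another study at any time. One is an entry criterion and the other a discretionary on-study criterion; both can apply.
- **9.6 contradicts 8.5.** Section 9.6 counts a subject as discontinued only if "the subject or his/her representative must notify the investigational site in writing, by telephone, or in person" and no later data are obtained, while 8.5 also covers subjects withdrawn by others. This is loose terminology to be tidied rather than a proven conflict.

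**Conclusion.** The point holds as a gap in the rules on data collection. As written, the plan requires (9.2) or permits (8.5) the exit of implanted subjects found ineligible, permits it for some adverse events or another study, and then ends their protocol data collection even if they still consent. The 12-month serum and later safety data can be lost while the discs stay in place.

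Each such loss is 3.3% of the planned 30. The effect on precision is small, and the issue is possible selective loss. A reader might infer that the 12-month results will be biased. The documents do not show that: they give no exit rate, and ineligibility or joining another study need not relate to outcome. The adverse event trigger is the one plausibly linked to it. The bias and success-rate figures above rest on assumed numbers lost and assumed differences, and the success-rate example concerns a secondary outcome.

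**What to change.** - In 9.2, and in the ineligibility item of 8.5, limit the exit to subjects found ineligible before implantation, with the same verb in both places.
- Keep implanted, consenting eligibility violators on the existing Table 2 schedule, including the 12-month serum. Record the deviation, analyse them in the primary set, and exclude them from the per-protocol set only, as SAP 7.1.3.2 already allows.
- For the adverse event and other-study items, reconcile 8.5 and 9.6 with 6.2, 11.1.2 and 11.1.3. The protocol should separate withdrawal from the study from the end of data collection, and say which applies to an implanted subject who still consents. The clinical criterion for withdrawal itself is for the sponsor and investigators to settle; no change to it is proposed here.
- Report exits by reason and by timing relative to surgery.

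The cost is amendment wording in 8.5, 9.2 and 9.6, one disposition table, and a few subjects completing visits already planned for them.

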## 9.3 Study Procedures

### Preoperatively:

- The patient will be asked to provide basic demographic and medical history data (including cancer history).
- The patient will be asked to provide information about his/her nicotine use, employment/work status, pain medication use (including chronic nonsteroidal anti-inflammatory drug (NSAID) use).

### Medtronic Controlled Information

- The patient will undergo the following assessments: Neck Disability Index (NDI), Neurological Status and Neck & Arm Pain.
- The patient will undergo an abbreviated physical examination.
- The patient will have a blood serum sample drawn for laboratory analysis to assess the Ti, Al and V metal concentration prior to the devices being implanted.

**Surgery/Discharge Visit:**

- Surgery data (i.e., estimated blood loss [including whether a transfusion was performed], length of surgery, and length of hospital stay) will be collected
- Any reported AEs will be documented.

## **9.4 Follow up Procedures**

**Follow up visits (6 week, 3 month, 6 month, 12 month):**

- The patient will be asked about his/her nicotine use, employment/work status, pain medication use (including chronic NSAID use).
- The patient will undergo/complete the following assessments: NDI, Neurological status, and Neck and Arm Pain. The patient will be asked if they have experienced any AEs, second surgery procedures, or other protocol-specified events of interest (e.g., cancer, pregnancies).
- The patient will have a blood serum sample drawn for laboratory analysis to assess the Ti, Al and V metal concentrations at preoperative, 6 week and 12 month follow up visits.

## **9.5 Unscheduled Visits**

For this study, only visits as designated per the "Schedule of Events" will be required. However, if any AEs or second surgeries are identified during the study, these will be reported.

